#### Oral NSAID Study Drug

Overall treatment compliance to oral NSAID study drug is defined as the total oral dose actually taken divided by the expected total oral dose of treatment during the treatment exposure period up to patient discontinuation from the treatment phase. It is calculated according to the following formula based on the NSAID/Placebo Dispensing/Accountability eCRF:

$$\frac{\sum_{\text{all treatment visits}} (\text{Number of pills dispensed} - \text{Number of pills returned})}{(\text{date of last dose of oral study drug} - \text{date of first dose of oral study drug} + 1) * 2} \times 100$$

Overall treatment compliance to oral study drug during the On-Treatment Period will be summarized descriptively by treatment group based on the SAF.

### **5.6.2. Exposure to Study Drugs**

The duration of treatment exposure to fasinumab and placebo SC doses will be calculated as:

= (Date of last SC injection of study drug in the on-treatment period – date of the first SC injection of study drug administration in the on-treatment period) + 28

The duration of treatment exposure to oral study drug will be calculated as:

= (Date of last dose of oral study drug in the on-treatment period – date of first dose of oral study drug in the on-treatment period) + 1

The duration of exposure will be summarized by treatment group using descriptive statistics based on the SAF.

The number and percentage of patients exposed to study drug will be presented by specific time period for each treatment group based on the SAF. The time periods of interest are specified as:  $\geq 1$  day,  $\geq 29$  days,  $\geq 57$  days,  $\geq 85$  days,  $\geq 113$  days,  $\geq 141$  days,  $\geq 169$  days.

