## 7. STUDY TREATMENTS

### 7.1. Investigational and Reference Treatments

Study drug in this study includes fasinumab, NSAID (diclofenac or celecoxib), and their matching placebo. Fasinumab and its matching placebo are SC study drug. NSAID (diclofenac or celecoxib) and its matching placebo are oral study drug.

Fasinumab drug product is supplied for this study in the following concentrations:

- Fasinumab 2 mg/mL: Each 1 mL single use pre-filled syringe delivers 0.5 mL of a 2 mg/mL solution (1 mg dose) of study drug
- Fasinumab-matching placebo: Each 1 mL single use pre-filled syringe delivers 0.5 mL of placebo solution
- Celecoxib (200 mg capsules), diclofenac (75 mg capsules) and NSAID-matching placebo capsules will be provided by the sponsor. All NSAIDs and NSAID-matching placebo will be over-encapsulated to preserve the blind.

Patients will be randomized 2:1:1:1 to receive 1 of the following treatment regimens:

- Fasinumab 1 mg SC Q4W and NSAID-matching placebo oral, twice daily
- Fasinumab-matching placebo SC Q4W and diclofenac 75 mg oral, twice daily
- Fasinumab-matching placebo SC Q4W, celecoxib 200 mg oral once daily, and NSAID-matching placebo oral once daily
- Fasinumab-matching placebo SC Q4W and NSAID-matching placebo oral, twice daily

All patients will receive SC injections of fasinumab or fasinumab-matching placebo. All SC injections will be in the abdomen, thigh or upper arm. Patients will be observed in the clinic for approximately 1 hour after study drug is administered. Patients randomized to earlier versions of the protocol with 3 mg SC Q4W or 6 mg SC Q8W fasinumab must be discontinued from study drug for the remainder of the study and will move directly into the follow-up period.

NSAIDs or NSAID-matching placebo will be administered orally. A proton pump inhibitor or other gastric protective medication may be prescribed if deemed medically necessary by the investigator or sub-investigator.

Doses of SC study drug must be given within  $\pm 7$  days from the scheduled dose date. If the window is missed, the SC dose of fasinumab or fasinumab-matching placebo should not be administered, however, the oral dose of NSAID or NSAID-matching placebo should be dispensed. The next SC dose of fasinumab or fasinumab-matching placebo should be administered at the next scheduled dosing date.

Detailed instructions for study drug dose administration are provided in the pharmacy manual.

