## 2. INVESTIGATION PLAN

### 2.1. Study Design and Randomization

This study is a randomized, double-blind, placebo- and NSAID-controlled study designed to evaluate the efficacy and safety of fasinumab in patients with OA of the knee or hip who have a history of inadequate pain relief with acetaminophen/paracetamol and a history of intolerance to or inadequate pain relief with opioids (or are unwilling to take opioids or have lack of access to opioids). The study consists of a screening period of up to 30 days, a 7 to 10 day pre-randomization/washout period (7 days with a +3 day window), a 24-week treatment period (with the last Q4W dose of study drug administered at week 20), a 20-week follow-up period, and a final phone call approximately 52 weeks after the last SC dose of study drug (Figure 1).

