### **5.6.3. Length of Study Observation**

The length of study observation will be calculated as:

= (Date of the last study visit[up to the End of Follow-up Clinic Visit] – date of the first study drug administration) + 1

The length of total study participation will be calculated as:

= (Date of the last study visit[up to the End of study phone call] – date of the first study drug administration) + 1

The lengths of study observation and total study participation will be summarized by treatment group using descriptive statistics based on the SAF.

The number and percentage of patients with observation and participation periods will be presented by treatment group based on the SAF. The time periods of interest are specified as:  $\geq 1$  day,  $\geq 29$  days,  $\geq 57$  days,  $\geq 85$  days,  $\geq 113$  days,  $\geq 141$  days,  $\geq 169$  days,  $\geq 197$  days,  $\geq 225$  days,  $\geq 253$  days,  $\geq 281$  days,  $\geq 309$  days).

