### **Date of first/last injection**

Date of first injection is the first non-missing start date of dosing filled in the ‘SC Study drug Injection’ CRF module.

If a patient’s date of the last dose is totally missing or unknown, his/her last visit date in the treatment period will be substituted.

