**Table 1: Analysis Windows**

Visit Number	Visit Name	Targeted Study Daysa	Analysis Window in Study Days
1	Screen	Day -30 to Day -11	[-30, -11]
2	Pre-randomization	Day -10 to -7	[-10, -1]
3	Baseline	1	1
Phone 1	Week 2	15	[2, 22]
4	Week 4	29	[23, 43]
5	Week 8	57	[44, 71]
6	Week 12	85	[72, 99]
7	Week 16	113	[100, 127]
8	Week 20	141	[128, 155]
9	Week 24	169	[156, 196]
10	Week 28	197	[197, 267]
11	Week 44	309	[268, 407]
Phone 2	Week 72	505	≥ 408

a Study days are calculated from the first dose of study drug (Day 1).

If multiple measurements occur within the same visit window, the following rules will be used to determine the analysis value:

- When multiple valid measurements occur within the same visit window, the one closest to the target study day will be used in the analysis.
- When multiple valid measurements occur within equal distance from the target study day, the value after the target study day will be used in the analysis.

Both scheduled and unscheduled measurements will be considered for determining abnormal/PCSV values from laboratory, vital sign or ECG as well as the baseline values.

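### SAP 5.6.2 puts one list of cut-points under two exposure formulas; six on-schedule SC injections give 168 days and miss the ≥169-day row by one day

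*SAP*

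**What the plan says.** SAP 5.6.2 gives two duration formulas. For SC study drug it is the last injection date minus the "date of the first SC injection of study drug administration in the on-treatment period) + 28". For oral study drug it is the last dose date minus the "date of first dose of oral study drug in the on-treatment period) + 1".

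The section then tabulates the number and percentage of patients exposed to study drug at ≥1, ≥29, ≥57, ≥85, ≥113, ≥141 and ≥169 days. It does not say which formula these rows use. Protocol 7.1 defines the term broadly: "Study drug in this study includes fasinumab, NSAID (diclofenac or celecoxib), and their matching placebo". Protocol 10.4.4.3 gives only the +28 formula and leaves the time periods to the SAP.

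The list in SAP 5.6.3 begins with the same seven values. There the length of observation is the last visit date minus the "date of the first study drug administration) + 1".

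**The concern.** From ≥29 upwards the cut-points equal the target study days of weeks 4 to 24 in SAP Table 1, that is 1 + 28k. A +1 formula returns the study day itself, so these thresholds fit it. The SC formula returns multiples of 28 for on-schedule dosing, one day below each threshold.

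For the rows up to ≥141 the next injection carries the patient over. The top row has no next injection, because SAP 2.1 describes the treatment period "with the last Q4W dose of study drug administered at week 20". A reader would naturally take the longest SC row as full 24-week exposure. As written, it leaves out patients who received every injection on the planned day, and it can include patients who received fewer.

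**Working it through.** **Inputs**

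- SC duration = (last injection day − first injection day) + 28; oral duration = (last dose day − first dose day) + 1 (SAP 5.6.2).
- Injections at baseline and weeks 4, 8, 12, 16 and 20, on days 1, 29, 57, 85, 113 and 141 (Schedule of Events; SAP Table 1). The first dose is day 1.
- SC dosing window ±7 days (Protocol 7.1), so the sixth injection can fall on days 134 to 148.

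**On-schedule SC exposure.** With the last of k injections on day 1 + 28(k − 1), duration = 28(k − 1) + 28 = 28k.

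| Injections | Last injection day | SC duration | Highest row reached | Next cut-point |
|---|---|---|---|---|
| 1 | 1 | 28 | ≥1 | 29 |
| 2 | 29 | 56 | ≥29 | 57 |
| 3 | 57 | 84 | ≥57 | 85 |
| 4 | 85 | 112 | ≥85 | 113 |
| 5 | 113 | 140 | ≥113 | 141 |
| 6 | 141 | 168 | ≥141 | 169 |

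Every duration is one day short of the next cut-point. No on-schedule patient reaches ≥169.

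**Using the window.** A sixth injection on days 134 to 148 gives 161 to 175 days. Reaching 169 needs day 142 or later (142 − 1 + 28 = 169). Days 134 to 141 give 161 to 168 and are left out. Among six-dose patients the row therefore separates late last injections from on-time or early ones.

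**Patients who reach the row without six injections**

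- Protocol 7.1 has an out-of-window dose skipped, after which "The next SC dose of fasinumab or fasinumab-matching placebo should be administered at the next scheduled dosing date". Five injections with a middle one skipped and the last on day 143 give 143 − 1 + 28 = 170 days.
- If the last-dose date is missing, SAP 6.4 says "his/her last visit date in the treatment period will be substituted". A week 24 visit on day 169 gives 169 − 1 + 28 = 196 days.

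**Oral comparison.** A last capsule on day 169 gives 169 − 1 + 1 = 169 and meets the row. A last capsule on day 168 gives 168 and does not.

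**Size.** The documents give no visit-timing data.

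- Bounds: none of the six-dose patients is left out if every last injection is late; all are left out if every one is on time or early.
- Assumed uniform timing over the 15-day window: 7/15 (47%) would reach ≥169.
- Limiting case with the plan's own figures: 600 × 0.80 = 480 fasinumab patients after 20% dropout. If all 480 had six injections exactly on schedule, the row would show 0/600 at ≥169 and 480/600 (80%) at ≥168. This treats dropout as the only reason for missed injections and uses the number randomized, whereas the table is on the safety set.

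**The case against.** The strongest objection is that no number is wrong. A ≥169-day row properly excludes a 168-day value, and the SAP never says that the row means a completed SC course. The list also follows the oral formula most closely and may have been meant for oral drug only. That reading cannot be ruled out, but it is the weaker one: the text says study drug, which covers both, and the protocol promises the time periods directly after the +28 formula.

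Other points stand as limits:

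- Full dosing can be recovered from the injection-count table in SAP 5.6.1, and the duration statistics would show values near 168.
- The five-dose and substituted-date cases arise from any last-minus-first formula and would remain in the top row after the cut-point changed.
- The 0/600 illustration is an extreme case.
- The oral row is not secure either. Visit timing moves patients across it (the week 24 window is days 162 to 176), and the documents do not say whether a capsule is taken on day 169.
- The mismatch could be placed in the +28 convention instead, since the on-treatment period in SAP section 5 runs from day 1 to day 169 for an on-schedule patient, 169 days counted inclusively. The protocol uses the same +28, however, so changing the cut-points is the smaller step.

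None of this removes the one-day shortfall for SC exposure.

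**Conclusion.** The point holds, at minor severity. Read as applying to SC exposure, the list places a patient with all six injections on schedule at 168 days, outside the ≥169 row, while a patient with five injections and a last dose on day 143 is inside it. The arithmetic is certain; the consequence depends on the list covering SC drug, which is the more natural reading. Every arm receives SC injections, so the offset applies to all of them. It affects one row of a descriptive exposure table and no efficacy, power or time-to-event result.

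**What to change.** For SC exposure, change the top cut-point from ≥169 to ≥168 days. A cleaner alternative is an SC-specific list of ≥1, 28, 56, 84, 112, 140 and 168 days, in which each row 28k matches k on-schedule injections; if only the top row changes, ≥141 and ≥168 both require six on-schedule injections. Keep the present values for the +1 formulas (oral exposure in 5.6.2, and 5.6.3), and state which formula each block of the table uses.

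Add a footnote that the ≥168 row still omits six-dose patients whose last injection was 1 to 7 days early (161 to 167 days), can include patients with a skipped dose or a substituted last-dose date, and should be read with the injection counts in 5.6.1. If the list was intended for oral study drug only, one sentence saying so is enough.

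The cost is a line of SAP text, separate row labels and a footnote. SC and oral rows would no longer share cut-points. Data collection, sample size and testing are unchanged.

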### **5.6.3. Length of Study Observation**

The length of study observation will be calculated as:

= (Date of the last study visit[up to the End of Follow-up Clinic Visit] – date of the first study drug administration) + 1

The length of total study participation will be calculated as:

= (Date of the last study visit[up to the End of study phone call] – date of the first study drug administration) + 1

The lengths of study observation and total study participation will be summarized by treatment group using descriptive statistics based on the SAF.

The number and percentage of patients with observation and participation periods will be presented by treatment group based on the SAF. The time periods of interest are specified as:  $\geq 1$  day,  $\geq 29$  days,  $\geq 57$  days,  $\geq 85$  days,  $\geq 113$  days,  $\geq 141$  days,  $\geq 169$  days,  $\geq 197$  days,  $\geq 225$  days,  $\geq 253$  days,  $\geq 281$  days,  $\geq 309$  days).

## **5.7. Analyses of Efficacy Variables**

Unless stated otherwise, all efficacy analyses will be based on the FAS. Confidence intervals will be constructed with level of confidence equal to 95%. With the exception of analyses based on the PPS, models including stratifying variables will utilize the value of these variables as captured in the IWRS system.

### 5.7.1. Analysis of Primary Efficacy Variable(s)

The co-primary efficacy variables are:

1. Change in the WOMAC pain subscale scores from baseline to week 24
2. Change in the WOMAC physical function subscale score from baseline to week 24

The following hypotheses will be tested:

- $H_1$ : There is no treatment difference between fasinumab 1 mg Q4W and placebo in WOMAC pain or physical function subscale at week 24 versus there is treatment difference in WOMAC pain and physical function subscale score at week 24

For  $H_1$ , the estimand is the difference in means between the fasinumab 1 mg Q4W dose+ protocol-defined rescue medication and placebo+ protocol-defined rescue medication in the change from baseline to week 24 in the WOMAC pain and physical function scores in the FAS, regardless of whether or not rescue medication or prohibited medication had been taken. Any data collected after discontinuing treatment will not be used in the primary efficacy analysis, but used in a treatment policy sensitivity analysis.

The co-primary efficacy variables will be analyzed separately using a multiple imputation approach with a mixed-effect model for repeated measures (MMRM) based on the FAS. For patients who discontinued treatment due to lack of efficacy or AEs or deaths, their missing WOMAC subscale scores after discontinuation will be imputed with values centered at the mean baseline WOMAC subscale score of the treatment group that the patient was randomized to. For patients who discontinued treatment due to other reasons including discontinuation because of public health measures implemented in response to COVID-19, their missing WOMAC subscale scores after discontinuation will be imputed under the missing-at-random assumption using the regression method with adjustment for covariates including treatment group, randomization strata (K-L category [2 to 3, or 4], index joint [knee, hip], and geographical region [Other, Europe, North America]) and baseline WOMAC subscale score. Intermittently missing WOMAC subscale scores prior to treatment discontinuation will be imputed using the Markov Chain Monte Carlo method.

Missing data up to week 24 will be imputed 50 times to generate 50 complete data sets by using the SAS procedure PROC MI following the 3 steps below:

- Step 1: The monotone missing pattern is induced by Markov Chain Monte Carlo (MCMC) method in MI procedure using seed number 4751688. Any score imputed outside the range of the WOMAC subscale score of 0-10 will be truncated to the nearest permissible value on the WOMAC scale according to the following algorithm:
  - If the imputed score  $> 10$ , then the final imputed score will be 10.
  - If the imputed score  $< 0$ , then the final imputed score will be 0.
- Step 2: The missing WOMAC subscale scores at visits subsequent to treatment discontinuation will be imputed using the regression method for the monotone pattern with seed number 4751688 and adjustment for covariates including treatment groups, randomization strata (K-L category [2 to 3, or 4], index joint [knee, hip], and

geographical region [Other, Europe, North America]), baseline WOMAC subscale score and all WOMAC subscale scores at preceding visits. Scores that are imputed outside the range of the WOMAC subscale will be truncated in the same manner as in step 1. As the regression method imputes missing data sequentially by visits, the truncation will be implemented after each visit iteration.

- Step 3: For patients who permanently discontinued study treatment due to lack of efficacy, death or AEs, the initially missing and now imputed WOMAC subscale scores at visits subsequent to treatment discontinuation will be adjusted to be centered at the mean baseline value for that treatment group, i.e., imputed score = initial imputed score under MAR – (mean change from baseline subscale score at the post-baseline time point for the treatment group based on patients on treatment with non-missing data at that time point). Scores that are adjusted to outside the range of the WOMAC subscale will be truncated in the same manner as in step 1.

Each imputed data set will be analyzed using a MMRM with terms for baseline WOMAC subscale score, randomization strata (K-L category [2 to 3, or 4], index joint [knee, hip], and geographical region [Other, Europe, North America]), treatment, visit, and treatment-by-visit interaction. The MMRM will be fitted using the MIXED procedure in Statistical Analysis System (SAS) with an unstructured covariance matrix to model the within-patient errors. The denominator degrees of freedom will be estimated using Kenward-Roger's approximation. In the event a model cannot be fit due to the estimation algorithm failing to converge, the covariance matrix for within-patient errors will be modeled by an autoregressive 1 structure, followed by a compound symmetry structure if convergence is still not achieved for the prior.

The results from the 50 analyses will be combined using Rubin's formulae (PROC MIANALYZE). The least squares means estimates for the mean change from baseline to week 24, as well as the difference of these estimates between fasinumab and placebo will be provided along with the corresponding standard error, p-value and associated 95% confidence interval. Similar estimates at other visits will also be presented.

The hypothesis for  $H_1$  will be rejected when the p-values corresponding to the difference in change from baseline to week 24 between fasinumab 1 mg Q4W and placebo is less than the available  $\alpha_0$  (see Section 5.7.4) for both the WOMAC pain subscale score and physical function subscale score.

### **Sensitivity analysis:**

Three sensitivity analyses will be performed to assess the robustness of the results generated for the primary efficacy analysis.

#### Analysis of Treatment Policy Estimand

Sensitivity analysis of the treatment policy estimand for the co-primary endpoints will be performed using similar analysis methods as the primary efficacy analysis. The treatment policy estimand is the difference in means between each fasinumab dose+ protocol-defined rescue medication and placebo+ protocol-defined rescue medication in the change from baseline to week 24 in the WOMAC pain and physical function scores based on the FAS, regardless of study treatment discontinuation prior to week 24 and regardless of whether or not rescue medication or prohibited medication had been taken. Hence, data from all patients, including

data collected after discontinuing treatment up to week 24 will be used in this sensitivity analyses. Missing WOMAC subscale scores up to week 24 will be imputed using the same approach as in Section 5.7.1.

### Tipping Point Analysis

Sensitivity analysis using a tipping point approach with multiple imputation will be performed to assess the robustness of the results due to data that may be missing not-at-random (MNAR).

This approach will introduce a sensitivity parameter,  $\delta$ . Estimations will be performed using multiple imputation methodology. Missing data up to week 24 timepoint will be imputed 50 times to generate 50 complete datasets by using SAS procedure PROC MI for each  $\delta$  following the 2 steps below:

- Step 1: The monotone missing pattern is induced by Markov Chain Monte Carlo (MCMC) method in MI procedure using seed number 4751688. Any score imputed outside the range of the WOMAC subscale score of 0-10 will be truncated to the nearest permissible value on the WOMAC scale according to the following algorithm:
  - If the imputed score  $> 10$ , then the final imputed score will be 10.
  - If the imputed score  $< 0$ , then the final imputed score will be 0.
- Step 2: The missing WOMAC subscale scores at visits subsequent to treatment discontinuation will be imputed using the regression method for the monotone pattern with seed number 4751688 and adjustment for covariates including treatment groups, randomization strata (K-L category [2 to 3, or 4], index joint [knee, hip], and geographical region [Other, Europe, North America]), baseline WOMAC subscale score and all WOMAC subscale scores at preceding visits. Scores that are imputed outside the range of the WOMAC subscale will be truncated in the same manner as in step 1. As the regression method imputes missing data sequentially by visits, the truncation will be implemented after each visit iteration.
- Step 3: For missing data because of permanent study treatment discontinuation due to adverse events, deaths or lack of efficacy,  $\delta$  will be added to the imputed values ( $\delta = 0$  corresponds to the MAR assumption). Scores that are adjusted to outside the range of the WOMAC subscale will be truncated in the same manner as in step 1.

Each imputed data set will be analyzed using a MMRM model with terms for baseline WOMAC subscale score corresponding to the efficacy variable being analyzed, randomization strata (K-L category [2 to 3, or 4], index joint [knee, hip], and geographical region [Other, Europe, North America]), treatment, visit, and treatment-by-visit interaction. For each  $\delta$  the SAS MIANALYZE procedure will be used to generate valid statistical inferences by combining results from the 50 analyses using Rubin's formula. By progressively increasing  $\delta$ , the sensitivity analysis will explore the tipping points, e.g.,  $\delta$  value when the p-value for a treatment comparison is above 0.05. Results will be then summarized using summary tables and graphs.

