## 10. STATISTICAL PLAN

This section provides the basis for the statistical analysis plan (SAP) for the study. The SAP may be revised during the study to accommodate amendments to the clinical study protocol and to make changes to adapt to unexpected issues in study execution and data that may affect the planned analyses. The final SAP will be issued before the database is locked.

Analysis variables are listed in Section 4.

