### 10.4.3. Efficacy Analyses

#### 10.4.3.1. Primary Efficacy Analysis

The primary efficacy variables will be analyzed using multiple imputation approach with mixed-effect model for repeated measure (MMRM) based on the FAS with adjustment for missing data due to lack of efficacy or AEs assuming the WOMAC scores would on average return to baseline values. Data collected after discontinuing treatment up to week 24 will not be used in the primary efficacy analysis, but used in a treatment policy sensitivity analysis. The imputed data for patients discontinued from the study treatment due to lack of efficacy or AEs will be centered at the mean baseline value. The missing data for patients who discontinued treatment due to other reasons will be imputed under missing-at-random assumption.

Missing data will be imputed 50 times to generate 50 complete data sets. Each imputed complete data set will be analyzed using the MMRM with terms for baseline score corresponding to the efficacy variable being analyzed, randomization strata (K-L category [2 to 3, or 4], index joint [knee, hip], and geographical region), treatment (fasinumab 1 mg Q4W, NSAIDs or placebo), visit and treatment-by-visit interaction. The MMRM will be performed using the MIXED procedure in Statistical Analysis System (SAS) with an unstructured covariance matrix to model the within-patient errors. Denominator degrees of freedom will be estimated using Kenward-Roger's approximation. The results from the 50 analyses will be combined using Rubin's formulae (PROC MIANALYZE). The least-squares mean estimates for the mean change from baseline to week 24, as well as the differences of the estimates between fasinumab 1 mg Q4W and placebo, and between fasinumab 1 mg Q4W and pooled NSAIDs group, with their corresponding standard errors, p values and associated 95% confidence intervals, will be provided.

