Sensitivity analysis of treatment policy estimand for the co-primary endpoints will be performed using a similar analysis method as the primary efficacy analysis, including data collected after discontinuing treatment up to week 24. Sensitivity analysis using tipping point approach with multiple imputation will be performed to assess the robustness of the results due to data that may be missing not-at-random. Multiple imputation will be based on monotone missing data structure of the change from baseline score using regression method. Monotone missing data structure will be achieved using Markov Chain Monte Carlo method. After each imputation, a fasinumab patient's imputed data will subtract k (eg, 20%, 40%, 100%) times the treatment effect at each corresponding time point. By progressively increasing coefficient k, the sensitivity analysis will explore the tipping point, ie, the upper bound on the critical value of coefficient k at which conclusion from the primary analysis will be overturned ( $p > 0.05$ ). Sensitivity analyses using PPS will also be performed for the primary and selected secondary endpoints.

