#### 3.3. The Per Protocol Set (PPS)

The per protocol set (PPS) will include all randomized patients from the FAS who complete the 24-week treatment period and who do not have to be excluded due to relevant protocol deviations. The PPS will be used to perform sensitivity analyses for the primary and selected secondary endpoints.

Section 10.4 contains the list of protocol violations which lead to exclusion from the PPS and corresponding PDID.

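### The SAP tipping-point rule names no arm to receive delta and leaves other-reason dropouts at MAR, an unlisted departure from the protocol's fasinumab penalty

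*SAP*

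**What the plan says.** Protocol section 10 states: "This section provides the basis for the statistical analysis plan (SAP) for the study". In 10.4.3.1 it defines the tipping-point rule: "After each imputation, a fasinumab patient" has a penalty applied, in that the "imputed data will subtract k (eg, 20%, 40%, 100%) times the treatment effect at each corresponding time point". The arm is named. No reason for discontinuation is mentioned.

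SAP 5.7.1, Tipping Point Analysis, imputes all missing scores under MAR in Steps 1 and 2. Step 3 then adds a fixed delta to a subset only: "For missing data because of permanent study treatment discontinuation due to adverse events, deaths or lack of efficacy". No treatment group is named there, in the paragraph on increasing delta that follows, or in the summary table in SAP 10.1.

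In the primary analysis, discontinuations for adverse events, lack of efficacy or (in the SAP) death are centred at the baseline mean. For the rest, the protocol says: "The missing data for patients who discontinued treatment due to other reasons will be imputed under missing-at-random assumption". The SAP repeats this and widens the group: "For patients who discontinued treatment due to other reasons including discontinuation because of public health measures implemented in response to COVID-19".

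SAP 1.2.4 lists eight modifications to, or additions beyond, the protocol's statistical section. None concerns the tipping-point analysis.

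**The concern.** Three things changed between protocol and SAP without being recorded: the arm is no longer stated, a restriction by reason appears, and k times the treatment effect became a fixed delta. The first two determine what the analysis can show.

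**Arm.** A programmer could shift fasinumab only, following the protocol, or every arm, following Step 3 literally. The second reading is not far-fetched: Step 3 of the primary imputation uses the same list of reasons and adjusts every treatment group. A delta given to both arms largely cancels in the treatment difference, so a result that does not tip might show only that the arms had similar dropout for those reasons.

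**Reason.** The primary analysis already departs from MAR for adverse-event, death and lack-of-efficacy dropouts. The group it leaves at MAR is everyone else, and Step 3 never moves that group. The other planned sensitivity analyses of the co-primary mean changes do not depart from MAR for them either. The treatment-policy analysis uses observed off-treatment data, but for the remainder: "Missing WOMAC subscale scores up to week 24 will be imputed using the same approach as in Section 5.7.1". The per-protocol set keeps only patients "who complete the 24-week treatment period" and reuses the primary approach.

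At stake is the claim that the co-primary result is robust to data missing not at random.

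**Working it through.** **Inputs from the documents** (protocol 10.2, SAP 2.2): 600 fasinumab and 300 placebo patients, 20% dropout to week 24, difference 1.1, SD 2.4, two-sided 0.05. SAP 5.7.1 gives the 0-10 score range.

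**Assumptions:** the share of each arm missing for the SAP's reasons (pF, pC), since the documents give no split of the 20%; a smaller benefit of 0.6 and a borderline one of 0.45, for illustration; and, for the truncation check only, a baseline mean of 6.3 and a placebo change of -1.5 or -2.0.

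**Stated power first.** Completers are 480 and 240. SE = 2.4 x sqrt(1/480 + 1/240) = 0.190, and 1.1/0.190 = 5.80. Power is 0.9999, which agrees with the stated value of at least 99%.

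**Formulas.** With benefit b, and k = 1 if an arm is shifted and 0 if not (this k is only an indicator, not the protocol's k):

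- Difference(delta) = -b + delta x (pF x kF - pC x kC)
- SE² = sum over arms of [(SD² + p(1-p)(k x delta)²)/n + SD²(1/(0.8n) - 1/n)]
- Tip = first delta on a 0.05 grid from 0 to 10 with |z| < 1.96

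For the unrestricted fasinumab rule, pF = 0.20 and only fasinumab is shifted.

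**Tipping delta before truncation:**

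| pF / pC | Benefit | Both arms, SAP reasons | Fasinumab only, SAP reasons | Fasinumab only, all missing |
|---|---|---|---|---|
| 10% / 10% | 1.1 | none | 6.95 | 3.6 |
| 8% / 12% | 1.1 | none | 8.6 | 3.6 |
| 12% / 8% | 1.1 | none | 5.85 | 3.6 |
| 15% / 5% | 1.1 | 6.55 | 4.7 | 3.6 |
| 10% / 10% | 0.6 | none | 2.25 | 1.15 |
| 8% / 12% | 0.6 | none | 2.8 | 1.15 |
| 12% / 8% | 0.6 | 4.65 | 1.9 | 1.15 |
| 15% / 5% | 0.6 | 2.2 | 1.55 | 1.15 |

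Two entries by hand, benefit 1.1:

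- All missing, delta 3.6: -1.1 + 3.6 x 0.20 = -0.38; SE 0.199; z = -1.91, so it tips.
- 10% / 10%, fasinumab only, delta 6.95: -1.1 + 6.95 x 0.10 = -0.405; SE 0.208; z = -1.95, so it tips.

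**Both arms shifted, equal shares (10% / 10%).** The difference stays fixed. z weakens only through added variance: at delta 10, from -5.80 to -3.87 (benefit 1.1) or from -3.16 to -2.11 (benefit 0.6). A benefit of 0.45 tips at about 6.1 on variance alone.

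**Both arms shifted, more such dropout on placebo (8% / 12%).** At delta 3 the difference is -1.1 + 3 x (0.08 - 0.12) = -1.22, and z moves from -5.80 to -6.08. With benefit 0.6 the difference moves to -0.72 and z from -3.16 to -3.59. The stress strengthens the result.

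**With 0-10 truncation**, benefit 1.1, 10% / 10%, placebo change -1.5 / -2.0 (normal week-24 scores limited to 0-10 before and after the shift, means and variances by numerical integration, same SE structure):

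- both arms: none / none
- fasinumab only, SAP reasons: none / 8.55
- fasinumab only, all missing: 3.55 / 3.4

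This is a single-visit approximation, not the planned MMRM with multiple imputation. It shows the ordering of the rules, not the figures the trial would report.

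**The case against.** Five points can be made for the plan.

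- **The arm can be inferred.** The SAP is based on the protocol, which names fasinumab, and increasing delta in search of a tip makes most sense against the active arm. This is the likelier intention, but it is not written, and primary Step 3 points the other way. Even if accepted, it settles only the arm.
- **The reason restriction is a legitimate choice.** The protocol never states that its rule covers every reason; that is read from the absence of a limit. Concentrating the stress on outcome-related discontinuations mirrors the primary analysis, and the SAP may revise the protocol. All true, but a revision belongs in SAP 1.2.4, and this one stresses again the group already handled conservatively while sparing the group left at MAR.
- **Other analyses treat all missing data alike.** The 30% responder test (H3) and the other WOMAC responder analyses count missing as non-response, and SAP 10.1 adds a sensitivity analysis for the 30% pain responder endpoint that treats anyone stopping treatment early as a non-responder. These do depart from MAR for any reason, but they do not test the co-primary mean differences.
- **The conclusion looks safe at the planning values.** The strictest rule tips at 3.6 points, about 3.3 times the assumed effect, whereas the protocol's examples stop at 100%. At 100% the difference is -1.1 + 0.20 x 1.1 = -0.88 (z about -4.6); with benefit 0.6 it is -0.48 (z about -2.5). This stands: no reversal is predicted. The protocol sets no cap on k, however, and the observed effect may be smaller than planned.
- **A fixed delta after discontinuation is not the protocol's rule either.** Correct. That is why the replacement should be recorded.

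**Conclusion.** The concern holds. Step 3 names no arm, restricts delta by reason where the protocol does not, and SAP 1.2.4 records neither change. At the planning values with an assumed 10% / 10% split and no truncation, the three readings give no tip, 6.95 and 3.6 points on the same data. With both arms shifted, more such dropout on placebo makes the result look stronger as delta rises; clearly more on fasinumab (15% / 5%) lets it tip at 6.55. On either arm reading, other-reason dropouts are never stressed in any planned analysis of the co-primary means.

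The sizes rest on assumed splits, since the documents give only total dropout, the difference and the SD. The ordering, with the unrestricted fasinumab-only rule tipping first, is the same across every split examined and under truncation. The analysis is supportive, so the H1 test, alpha control and sample size are untouched. It should be fixed before unblinding, so that the reading cannot be chosen after the result is known.

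**What to change.** Replace the Step 3 rule with wording such as: *A worsening delta (>0) is added to the imputed values of fasinumab patients only, for all post-discontinuation missing data regardless of reason.* A grid with a separate delta for each arm, over the same data, is an acceptable alternative.

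Report the number of patients shifted, by arm and reason. Record in SAP 1.2.4 that a fixed delta replaces the protocol's multiple of the treatment effect, together with any restriction by reason that is kept. Starting from the primary imputation instead of MAR is optional. Editorially, state the delta grid and correct the step count, which is announced as two although three steps are given.

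The cost is SAP wording, one entry in 1.2.4 and minor reprogramming of one sensitivity analysis. The robustness statement may become less favourable.
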